8.3.2 Secondary Outcome Measures

Secondary outcomes during PICU stay:

- Time to achievement of target energy requirement
- Time to achievement of target protein requirement
- Diagnosis of Ventilator Associated Pneumonia
- Diagnosis of necrotising enterocolitis in infants
- Duration of time with no enteral feed in the first 7 days after randomisation
- Incidence of vomiting leading to feed stoppage in the first 7 days after randomisation
- Documented healthcare acquired infections

Secondary outcomes assessed at PICU discharge:

• Length of PICU stay (days)

Longer terms secondary outcomes (post-PICU discharge):

- Mortality at 30 days and 6 months post randomisation
- Length of hospital stay
- Health-related Quality of Life (assessed using PedsQL and CHU-9D questionnaire data)
- Feeding component of the Functional Status Score

These outcomes are consistent with core outcomes recommended for PICU trials (26) and this is consistent with our feasibility work consulting with parents and clinicians.

Cost-effectiveness outcomes

- Resource use and costs
- Total costs at six months.
- Quality-Adjusted Life Years (QALYs) at six months.
- Incremental net monetary benefits calculated at £20,000 per QALY at six months associated with intervention (No routine GRV measurement) versus control (standard GRV measurement).

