8.3.3 Outcome Definitions

NECROTISING ENTEROCOLITIS (NEC): as a new diagnosis after randomisation for children who are under 1 year old. The diagnosis is to be based on a combination of systemic, abdominal and/or radiological signs.

- Systemic signs Include temperature instability, apnoea, bradycardia, raised inflammatory markers, thrombocytopenia, shock features. In NEC these are present with abdominal and or radiological signs stated below.
- Abdominal Intestinal signs include abdominal distension, reduced or absent bowel sounds, larger than normal gastric aspirates, gastric bleeding, rectal bleeding, abdominal tenderness, or cellulitis.
- Radiological signs The following are radiological signs of NEC and cases with these should be counted as a case of NEC: pneumatosis coli, portal gas, perforation – pneumoperitoneum (excluding air under the diaphragm associated with insertion of a PD catheter in theatre or in ICU, or accidental opening of the peritoneum during the operation).

A child who develops only mild systemic and/or abdominal-intestinal signs and is treated only with a 24-48 hour rule out course of NBM and antibiotics followed by re-starting feeds based on improvement should not be counted as a case of NEC.

If a general surgeon assesses the child and based on features from the systemic signs and abdominal signs elects to treat the child as NEC with NBM for minimum 5 days, then this case should be counted as a case of NEC.

Any child with a surgical abdomen who has a more serious picture – perforation, peritonitis, abdominal mass, is to be counted. There is no requirement for grading, however as a practical guide the following simplified classification has been suggested

- Moderate any child meeting the criteria who does not need surgery and survives.
- Severe a child with NEC who needs surgery and/or dies.

VENTILATOR ASSOCIATED PNEUMONIA (VAP): any new course of antibiotics prescribed for a presumed or proven VAP.

CATHETER RELATED BLOOD STREAM INFECTIONS (CLABSI): proven or suspected CLABSI leading to commencement or continuation of antimicrobials (Appendix 3).

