14.3 Recording and Reporting Procedures

The key safety outcomes in the GASTRIC-PICU trial are ventilator-associated pneumonia (VAP) and necrotising enterocolitis (NEC). Incidence of these events will be captured via the Case Report Forms and does not need to be reported additionally as SAEs.

Considering that all children eligible for the GASTRIC-PICU trial are critically ill and, due to the complexity of their condition, are at an increased risk of experiencing AEs – occurrences of SAEs will only be reported if they are considered to be possibly, probably or definitely causally related to the study (i.e., either as a consequence of measuring GRV, or not measuring GRV). Non-serious adverse events do not require reporting for trial purposes.

The reporting period is from the time of randomisation until 30 days post-randomisation or until final discharge from critical care unit (whichever is sooner).

All reportable SAEs (i.e., serious events which are considered possible, probably, or definitely related to the study) must be reported to ICNARC CTU within 24 hours of the site research team becoming aware of the event. Related events must be assessed for expectedness (against the list in Appendix 3). Staff should not wait until all information about the event is available before sending SAE notification. Information not available at the time of the initial report must be documented and submitted as it becomes available.

SAEs must be recorded in the patients' medical notes and reported to the ICNARC CTU using the GASTRIC-PICU SAE Reporting eCRF. If the eCRF is unavailable, the SAE report can be sent by email to [contact].

The process for recording and reporting adverse events and serious adverse events is summarised in Figure 1 (Adverse Event Reporting).

Figure 1. Adverse Event Reporting

*If there is any uncertainty about whether the SAE is associated with trial treatment, then it should be reported.

On receipt of an SAE report, a member of the ICNARC CTU will first evaluate the report for completeness and consistency. Then, a clinical member of the GASTRIC-PICU Trial Management Group (TMG) will evaluate the event to determine whether it requires expedited reporting to the Research Ethics Committee (REC). If the event is a related and unexpected SAE, the ICNARC CTU will submit a report to the REC within 15 calendar days.

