16.3.3 Analysis of secondary clinical endpoints

All secondary clinical endpoints will be reported in both the ITT and PP populations unless otherwise specified. Data for all feeding related endpoints (time to achievement of target feeds, time to achieve protein requirement, time with no enteral feeds) will be recorded up to and including 7 days post randomisation only.

Time to event endpoints (time to achieve target feeds, time to achieve target protein requirements) will be measured from randomisation and compared between arms using adjusted Cox proportional hazards regression models. Starting on the day after randomisation, achievement of target feeds is defined as a total calorie intake for a calendar day which is equal to (or more than) the target 24-hour calorie intake for the patient. Patients who do not meet this target will be censored at death, discharge from PICU, or on day 7 following randomisation (whichever is earliest). Time to achieve target protein requirement is measured in the same way.

Binary endpoints (diagnosis of ventilator associated pneumonia, diagnosis of necrotizing enterocolitis in infants, incidence of vomiting leading to feed stoppage, documented healthcare acquired infections,

mortality at 30 days and 6 months) will be reported by arm as counts and percentages and compared using adjusted logistic regression models. Diagnosis of ventilator associated pneumonia will additionally be reported as a rate per 1,000 hours of ventilation and compared between groups using an adjusted Poisson regression model. Survival to 6 months following randomisation will also be reported using a Kaplan-Meier plot and compared between groups using an adjusted Cox proportional hazards model.

Continuous endpoints (duration of time with no enteral feed, length of stay in PICU and in hospital, PedsQL and CHU-9D) will be summarised by arm using mean and standard deviation and compared between arms using adjusted linear regression models. Feeding component of Functional Status Score will be analysed as an ordinal endpoint, summarised by the number and percentage in each category and compared between groups using an adjusted proportional odds regression model.

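### Necrotising enterocolitis is a key safety outcome, but its severity need not be recorded and is not compared by arm, and the yes/no count is open to different ascertainment in the two arms

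*Protocol*

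**What the plan says.** All references are to the Protocol.

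- **Outcome.** Section 8.3.2 lists "Diagnosis of necrotising enterocolitis in infants". The schedule in section 13.1 likewise collects the diagnosis, at day 30.
- **Definition.** Section 8.3.3 builds the diagnosis from systemic, abdominal and radiological signs. One abdominal sign is "larger than normal gastric aspirates". A case without radiological signs counts if a general surgeon decides, on systemic and abdominal features, to treat it as NEC with at least 5 days nil by mouth. A mild episode that settles after a 24–48 hour rule-out course does not count.
- **Grading.** The same section states: "There is no requirement for grading, however as a practical guide the following simplified classification has been suggested". The upper of its two levels reads "Severe a child with NEC who needs surgery and/or dies".
- **Analysis.** Section 16.3.3 places NEC diagnosis among the binary endpoints, which "will be reported by arm as counts and percentages and compared using adjusted logistic regression models". No analysis uses the moderate/severe split.
- **Safety reporting.** Section 14.3 names ventilator-associated pneumonia and NEC as the key safety outcomes and adds: "Incidence of these events will be captured via the Case Report Forms and does not need to be reported additionally as SAEs". Appendix 2 lists NEC as an expected event.
- **Where consequences of NEC could appear.** Death by day 30 takes the worst rank in the composite (16.3.2). Mortality is compared at 30 days and 6 months (16.3.3). Treatment of NEC is costed as resource use (16.4).

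**The concern.** The trial asks whether a routine monitoring step can be dropped safely. For a key safety outcome, readers and the DMEC will want to know how many infants had NEC and how bad it was. The Protocol supplies a simple severity split and then makes it optional. A SAP cannot reliably analyse a grade that sites have been told they need not assign.

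The count that is analysed also depends partly on the allocation. Section 12.1 has intervention patients monitored by clinical signs and not by GRV, while section 12.2 has control patients aspirated at least every 6 hours. One of the listed diagnostic signs is thus routinely observed in one arm only, by staff who know the allocation (12.4). Milder, non-radiological NEC could be recognised more readily in control. Equally, wary clinicians could look harder in the intervention arm. Similar counts would not then establish similar disease, nor would different counts establish a difference. Surgery and death depend much less on whether an aspirate was taken.

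**Working it through.** The Protocol states no incidence, severity share or power for NEC, so there is no figure of its own to reproduce. The check has two parts.

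**1. Which route would show a difference in NEC severity between arms?**

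| Route | Shows NEC surgery? | Shows NEC death? |
|---|---|---|
| NEC diagnosis, yes/no (8.3.2, 16.3.3) | No | No |
| Serious adverse event report with the 14.2.3 severity scale | Not required (14.3) | Not required (14.3) |
| Composite and mortality (16.3.2, 16.3.3) | No | Yes, not attributed to NEC |
| Length of stay and costs (16.3.3, 16.4) | Indirectly | Indirectly |
| Grade in 8.3.3 | Optional, not analysed | Optional, not analysed |

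**2. How large could it be?**

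Inputs from the Protocol: target 4,700 and 5% withdrawal (16.1); at least half of PICU admissions under 12 months (7.1), taken as one half; mortality 4.2% (16.1).

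Assumptions, not in the Protocol: NEC incidence of 0.5–2% of infants for the case count and 1–5% for the power figures; 30% of cases severe in control against 50–60% in the intervention arm; the same number of cases in each arm.

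- Infants: 4,700 × 0.95 = 4,465; 4,465 / 2 ≈ 2,232; about 1,116 per arm.
- Total cases: 2,232 × 0.005 ≈ 11; 2,232 × 0.02 ≈ 45.
- At 2%: 1,116 × 0.02 ≈ 22 cases per arm. Severe cases are 22.3 × 0.30 ≈ 7 in control, against 22.3 × 0.50 ≈ 11 or 22.3 × 0.60 ≈ 13 in the intervention arm. The yes/no comparison stays at 22 v 22, odds ratio 1.0.
- Power of a two-proportion test on severe NEC per infant: 18–32% at 2% incidence, and 11–67% across 1–5%.
- Precision at 11 v 7: the ratio is 11/7 = 1.57. The standard error of its log is about √(1/11 + 1/7) = 0.483, so the 95% interval is 1.57 divided and multiplied by exp(1.96 × 0.483) = 2.58, that is 0.61 to 4.05.
- Dilution of deaths: if half to all of the extra severe cases died, all-cause mortality would rise by 0.05–0.75 percentage points on 4.2% across 1–5% incidence. Power to detect that is about 3–22%.
- Sensitivity of the count to ascertainment: if 4 of 22 cases in one arm went uncounted, the ratio would be 18/22 = 0.82 with no difference in disease.

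**The case against.** Four objections have force.

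- **Deaths are not lost.** A reader might infer that extra fatal NEC would go unseen. The documents do not support that. Every death by day 30 ranks worst in the composite, and mortality is compared at 30 days and 6 months. NEC and death are both held per patient, so fatal NEC by arm is a cross-tabulation of planned data. What remains is that no such comparison is named and that the mortality outcomes dilute it.
- **Delayed recognition is a hypothesis.** A reader might infer that not measuring GRV delays recognition and so raises severity without raising numbers. The Protocol neither states nor tests this; its rationale for GRV in section 7 is aspiration risk. The definition also cuts against it: if delay turned a mild, uncounted episode into established disease, the count itself would rise. The point made here does not need this mechanism.
- **Severity may be recorded somewhere.** Section 16.4 takes resource use for treating NEC from the case report forms, section 17.3 adds linked data, and the forms and SAP are not shown. The DMEC can set the basis on which it receives safety information (14.3). All true, but a form that requires the grade would conflict with 8.3.3, and costing is not a clinical comparison by arm.
- **The severe grade is imperfect.** It includes any death in a child with NEC, with no time window or attribution, and surgery is decided by unblinded clinicians. This stands. It is a reason to report the two parts separately and to fix a window. Surgery and death are less exposed to the aspirate problem, not immune to bias.

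**Conclusion.** The point holds as a modest, inexpensive improvement. The Protocol makes severity of a key safety outcome expressly optional, compares NEC by arm only as yes or no, and exempts it from the other route that would grade it. NEC surgery is therefore in no named clinical comparison, and NEC deaths appear only unattributed within all-cause mortality and the composite. The count that is compared rests in part on a sign routinely observed in one arm.

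The size is uncertain, because incidence and severe share are assumed. With 11–45 cases in total, even a marked shift would usually not be separable from chance: a 14 v 8 split of severe cases has a two-sided binomial p of about 0.29. The gain is a visible safety description that is less open to ascertainment bias. It is not a powered test and no evidence of harm. The co-primary analyses are unaffected.

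**What to change.** - **Section 8.3.3:** replace the statement that grading is not required with required recording, for every NEC case, of surgery for NEC (yes/no) and of death with its date, within a stated window such as the 30-day outcome period. Together these give the Protocol's own moderate/severe split.
- **Section 16.3.3:** report severe NEC, and surgery and death separately, by arm as counts and percentages with a confidence interval, labelled descriptive.
- **Section 14.3:** include the same figures in the safety information given to the DMEC.

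The cost is one case report form item for perhaps a few dozen children and a short entry in the safety table. Sites already know whether a child had surgery and whether the child survived, and 30-day survival is needed for the composite anyway. The remaining limits should be stated with the table: numbers will be small, and the severe category will include some deaths from other causes.

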9.1 Trial Design

GASTRIC-PICU is a multi-centre, randomised, non-inferiority trial with internal pilot phase and integrated health economic evaluation.

9.2 Internal Pilot

An internal pilot will run from months 7-16 of the grant timeline and use a traffic light system to assess key progression criteria regarding site opening, recruitment, and adherence to the study protocol (25). The internal pilot will follow the same processes as the main trial; participants enrolled in the pilot will be included in the analysis of the main trial.

We will use a traffic light system to assess progression from internal pilot stage to the full trial as below:

	Red	Amber	Green
Number of sites opened	<14	14-18	≥19
Patient recruitment relative to target	<85%	≥85 and <100%	≥100%
Non-adherence	>15%	>5% and ≤15%	≤5%

Non-adherence is defined as the percentage of all randomised patients who meet either of the following criteria:

- Randomised to no routine GRV measurement and have had one or more GRV measurements taken within the first three calendar days following randomisation (except for any measurement taken in response to a recorded clinical indication)
- Randomised to routine GRV measurement and no measurement has been taken in at least one whole calendar day spent in PICU following randomisation, up to and including the third day after randomisation

If all the green criteria are met, the trial will progress from the internal pilot to the full trial unchanged. If any of the amber criteria are met, we will consult the Trial Steering Committee (TSC) and we will act upon their advice to address the issues raised. If any of the red criteria are met, we will discuss urgently with the TSC and the funder and consider remedial actions, including discontinuation. An internal pilot report will be reviewed by the TSC, and any required remedial plans developed before a pilot phase report is submitted to the NIHR HTA.

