12.3 Concomitant Care

All other aspects of nutritional practice will be according to usual unit practice, including, but not limited to timing of commencement of feeds, speed of increase of enteral feeds and choice of feed.

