12.6 End of Treatment

For both groups, trial treatment will continue until tube feeds have been discontinued during the PICU admission or until discharge from PICU, whichever is sooner. The trial treatment will apply at any point the patient requires tube feeds during their PICU admission (for example, the patient will return to their assigned treatment group in the case of failed attempt to stop tube feeding). The decision to discontinue tube feeds is at the discretion of the clinical team.

13. Trial Procedures

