16.3 Clinical effectiveness analysis methods

16.3.1 General principles

All analyses will be outlined in a statistical analysis plan (SAP) approved by an independent trial steering committee and seen by the independent data monitoring committee.

The following analysis populations will be defined:

- Per protocol (PP), which will exclude patients where consent to data collection has been withheld or withdrawn before day 30, and also patients classed as non-compliant as defined previously for the pilot evaluation stage.
- Intention to treat (ITT), which excludes patients where consent to data collection has been withheld or withdrawn for all data processing.
- ITT (energy intake), which excludes patients where consent to data collection has been withheld before 72 hours or withdrawn for all data processing.

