16.3.2 Analysis of co-primary clinical outcomes

The composite outcome will be analysed using a proportional odds logistic regression model, with death during the first 30 days following randomisation ranked as the worst possible outcome (assigned value -1), and surviving patients assigned values according to their total calendar days free from mechanical ventilation during the first 30 calendar days following randomisation (with the day of randomisation counted as day 1). The model will be adjusted for important baseline variables including all variables used as stratification variables at randomisation. Baseline factors for inclusion in adjusted analyses will be selected a priori based on an established relationship with outcome for critically ill children, and not because of observed imbalance, significance in univariable analyses or by a stepwise selection method. The proportional odds assumption will be tested using Brant's test; however, it is noted that in the event that the proportional odds assumption is violated, the odds ratio retains an equivalent interpretation to alternative effect estimates using non-parametric, rank-based methods. The primary effect estimate will be the adjusted odds ratio, which will be calculated in both the PP and ITT populations with two-sided 95% confidence intervals. If the upper limit of the confidence interval is not more than 1.2 in both the PP and ITT populations, we will declare the intervention is non-inferior with respect to mortality and days free of ventilation by 30 days. Secondary analyses will test the same outcome for superiority/inferiority. The two separate components of the composite primary outcome will also be reported by arm.

Percentage of energy requirements met will be calculated in the ITT population, and for each patient is defined as the total calories consumed during the first 72 hours divided by the target calorie intake for the first 72 hours (capped at 100%). The primary effect estimate will be the difference in mean percentage of target achieved between the arms, which will be tested for superiority (at P<0.05) using a linear regression model adjusted for the same baseline variables as the analysis of the composite primary outcome. The primary effect estimate will be the difference in means, which will be reported with a two-sided 95% confidence interval.

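### The control-arm non-adherence rule counts PICU days after tube feeds have ended, so correctly treated control children leave the per-protocol set and one of the two required non-inferiority tests is biased

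*Protocol*

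**What the plan says.** Four parts of the protocol bear on this.

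- **Non-adherence (9.2).** A control child is non-adherent if "Randomised to routine GRV measurement and no measurement has been taken in at least one whole calendar day spent in PICU following randomisation". There is no condition that the child is being tube fed that day, and no exception. The rule looks at days "up to and including the third day after randomisation". The intervention-arm criterion is one or more GRVs in the first three calendar days, "except for any measurement taken in response to a recorded clinical indication".
- **When trial treatment applies (12.6).** In both arms "trial treatment will continue until tube feeds have been discontinued during the PICU admission or until discharge from PICU, whichever is sooner". The section adds: "The trial treatment will apply at any point the patient requires tube feeds during their PICU admission".
- **PP set (16.3.1).** It excludes patients whose consent to data collection was withheld or withdrawn before day 30, and "also patients classed as non-compliant as defined previously for the pilot evaluation stage".
- **Decision rule (16.3.2).** Non-inferiority is declared "If the upper limit of the confidence interval is not more than 1.2 in both the PP and ITT populations".

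On the start of feeds, 12.3 leaves to usual unit practice the "timing of commencement of feeds, speed of increase of enteral feeds and choice of feed", while 11.3 expects feeding to begin at randomisation.

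**The concern.** Sections 9.2 and 12.6 give opposite answers for the same child. Take a control child who is extubated, comes off tube feeds and then spends a whole calendar day in PICU inside the window. Trial treatment has ended under 12.6, so no GRV is due. Under 9.2 the missing GRV makes the child non-adherent, and 16.3.1 removes the child from PP.

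The same course cannot remove an intervention child, for whom having no GRV is adherence. The exclusion is therefore made after randomisation, acts in one arm only, and is linked to how soon the child leaves the ventilator, which is most of the composite outcome. Removing early-liberated controls makes the control arm look worse and moves the PP odds ratio towards non-inferiority.

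PP is one of two tests that must both pass, and 16.1 enlarges the trial to preserve its power. A PP set formed this way does not give the protection it is there for. The same children also count in the pilot non-adherence figure.

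**Working it through.** **Inputs.** From 16.1: margin OR 1.2; two-sided 95% CI; 90% power; 4.2% mortality; log-normal ventilation with median 2.9 days and lower quartile 1.0 day; 4,000 evaluable; 10% cross-over, 5% withdrawal, 4,700 in total. From 11.2: 1:1 allocation. From 16.3.2: death ranked worst, survivors ranked by ventilator-free calendar days, day of randomisation counted as day 1. *Assumed, because the documents do not say:* the share of early-liberated controls who spend a whole PICU day without a GRV because tube feeds have ended.

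**Step 1: the plan's own figure.** The log-SD is ln(2.9/1.0)/0.6745 = 1.579. With 31 ordered categories, the proportional-odds formula N = 12(1.960 + 1.282)² / [(ln 1.2)² (1 − Σp³)] gives 3,837 to 3,867, depending on how days are rounded and on whether control or averaged category shares are used. The stated 4,000 is this rounded up (power about 91%). Inflation: 4,000/0.85 = 4,706 or 4,000/(0.90 × 0.95) = 4,678, so 4,700 reproduces.

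**Step 2: who could be affected.** The third day after randomisation is calendar day 4. A child ventilated for at most 3 calendar days can therefore be off the ventilator for all of day 4. Under the 16.1 distribution, with time of randomisation spread evenly over the day, 44% of controls survive and fall in this group (49% if durations are simply rounded up).

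**Step 3: set sizes.** ITT per arm: 4,700/2 × 0.95 = 2,232. PP per arm with 10% other non-adherence: 2,232 × 0.90 = 2,009. The early group is 0.442 × 2,232 ≈ 986 controls.

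**Step 4: bias at the margin.** The true OR is set to 1.20, a fraction of the early group is removed from controls, and the proportional-odds model is refitted. The chance that PP passes is Φ[(ln 1.2 − ln OR)/SE − 1.96], with SE = √{(3/0.987)(1/n₀ + 1/n₁)}. For 10% lost: n₀ = 2,009 × 0.956 = 1,921, SE = 0.0556, OR = 1.110, so Φ[(0.1823 − 0.1044)/0.0556 − 1.96] = Φ(−0.56) = 29%. Simulation (20,000 trials per scenario) agrees to within about a percentage point.

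| Early group lost | Controls lost | OR seen in PP | PP passes falsely | PP and ITT both pass |
|---|---|---|---|---|
| 0% | 0 | 1.20 | 2.5% | 1.8% |
| 2% | 20 (0.9%) | 1.18 | 4.6% | 2.2% |
| 5% | 49 (2.2%) | 1.15 | 10% | 2.5% |
| 10% | 99 (4.4%) | 1.11 | 29% | 2.4% |

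**Step 5: with cross-over.** Suppose 10% of each arm crosses over and takes the other arm's outcome distribution (an assumption). A true on-treatment OR of 1.20 dilutes to 1.16 in ITT, which then passes falsely about 10% of the time. A sound PP set holds the joint rate at about 2.5%. With 2%, 5% or 10% of the early group also lost, the joint rate is about 4.4%, 7.9% or 10%.

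**Step 6: the reverse case.** If the controls lost are slower ones (dead, or ventilated more than 3 days) and the true OR is 1.00, losing 5% or 10% of them cuts PP power from 91% to about 74% or 45%.

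**Step 7: after the correction.** With no selective loss, the PP odds ratio returns to 1.20 at the margin with a false-pass rate of 2.5% to 2.7%, and PP power at OR 1.00 is 91%.

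**The case against.** **ITT still has to pass.** This stands. A reader might infer that the trial's false non-inferiority rate rises to 10% or 29%. The documents do not support that: 16.3.2 requires both sets, ITT is untouched by the 9.2 rule, and the joint rate in Step 4 stays at or below about 2.5%. It rises only when cross-over dilutes ITT (Step 5), which is the situation PP is meant to guard against and for which 16.1 budgets 10%.

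**The direction is not fixed.** This also stands. A reader might infer that every affected child is selected by recovery. That fits children whose tube feeds have ended. Children whose feeds have not started may be sicker (itself an assumption), and losing them biases PP the other way. Unit discretion under 12.3 makes such children possible, but 11.3 expects feeds to begin at randomisation and 10.1 requires an intention to feed by the gastric route, so this group is less likely. With equal proportional losses at both ends the effect nearly cancels: dropping 10% of controls alive and off the ventilator within 48 hours, together with 10% of the slower controls, makes a true OR of 1.20 read 1.21.

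**The share may be small.** This is fair. The child must stop tube feeds, not merely leave the ventilator, and then spend a whole calendar day in PICU; children discharged from PICU do not count. Eligibility also requires that extubation is not planned within 48 hours. But that is a plan at entry, and the window runs past 48 hours.

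**The pilot effect is modest.** Non-adherence is a percentage of all randomised patients. Even 99 children are about 2.2% of 4,464 (2 × 2,232). That could move the pilot figure from green to amber but is unlikely to decide it.

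**Conclusion.** The contradiction between 9.2 and 12.6 is on the face of the protocol, and 16.3.1 and 16.3.2 carry it into a test that must pass for non-inferiority. Applied as written, the rule removes correctly treated control children from PP in a way related to outcome and without a counterpart in the intervention arm. The intervention arm has its own exclusion for GRVs without a recorded indication, but ending feeds cannot trigger it.

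The size rests on a share that is not in the documents. Across 2% to 10% of early-liberated controls, a true OR of 1.20 reads 1.18 to 1.11 in PP, and PP alone passes falsely about 5% to 29% of the time. The main loss is the PP safeguard rather than the trial's overall type I error. If the excluded controls are mainly sicker and unfed, the cost is power instead. The net direction depends on an unknown mix. This should be corrected, but it does not by itself undermine the non-inferiority conclusion while ITT must also pass.

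**What to change.** Reconcile 9.2 and 16.3.1 with 12.6. For the control-arm rule only, count whole calendar days in PICU on which trial treatment is in force under 12.6:

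- Days after tube feeds have been discontinued, and days before they have started, do not count.
- Days on which feeds are only temporarily withheld still count. The example guidelines in Appendix 1 re-assess GRV while feeds are withheld, so excusing every unfed day would hide real lapses.
- Leave the intervention-arm rule unchanged. Restricting it to tube-fed days would overlook GRVs taken without an indication on other days.

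The change is a sentence in 9.2, picked up by reference in 16.3.1, and is best made before any results by arm are known. The one check needed is on data: 13.1 lists enteral feeding data at day 3 and day 7, and 16.3.3 uses total calorie intake by calendar day, but neither says that the record shows on which days tube feeding was in progress, withheld or ended. Confirm that it does. If not, a daily tube-feeding status up to the third day after randomisation would be needed.
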